## 5.3.3.3. Date of Death

Missing or partial death dates will be imputed based on the last contact date:

- If the date is missing, it will be imputed as the day after the date of last contact;
- If the day or both day and month is missing, death will be imputed to the maximum of the full (non-imputed) day after the date of last contact and the following:
  - Missing day: 1st day of the month and year of death;
  - Missing day and month: January 1st of the year of death.

## 5.3.3.4. Date of Start of New Anticancer Therapy

Incomplete dates for start date of new anticancer therapy (drug therapy, radiation with curative intent, transplant) will be imputed as follows and will be used for determining censoring dates for efficacy analyses and in the derivation of the end of the on-treatment period. PD date below refers to PD date by investigator assessment. If the imputation results in an end date prior to the imputed start date, then the imputed start date should be set to the end date.

- The end date of new anticancer therapy will be included in the imputations for start date of new anticancer therapy. If the end date of new anticancer therapy is
  - completely missing then it will be ignored in the imputations below;
  - partially missing with only year (YYYY) available then the imputations below will consider 31DECYYYY as the end date of the new anticancer therapy;
  - partially missing with only month and year available then the imputations below will consider the last day of the month for MMMYYYY as the end date of the new anticancer therapy.
- For participants who have not discontinued study intervention at the analysis cutoff date, last dose of study treatment is set to the analysis cutoff date in the imputations below.
- If the start date of new anticancer therapy is completely or partially missing, then the imputed start date of new anticancer therapy is derived as follows:
  - Start date of new anticancer therapy is completely missing
    - Imputed start date = min [max(PD date + 1, last dose of study intervention + 1), end date of new anticancer therapy]
  - Only year (YYYY) for start of anticancer therapy is available
    - IF YYYY < Year of min [max(PD date + 1, last dose of study intervention + 1), end date of new anticancer therapy]

THEN imputed start date = 31DECYYYY;

• ELSE IF YYYY = Year of min [max(PD date + 1, last dose of study intervention + 1), end date of new anticancer therapy]

THEN imputed start date = min [max(PD date + 1, last dose of study intervention + 1), end date of new anticancer therapy]

• ELSE IF YYYY > Year of min [max(PD date + 1, last dose of study intervention + 1), end date of new anticancer therapy]

THEN imputed start date = 01JANYYYY

- Both Year (YYYY) and Month (MMM) for start of anticancer therapy are available
  - IF YYYY = Year of min [max(PD date + 1, last dose of study intervention + 1), end date of new anticancer therapy], AND

MMM < Month of min [max(PD date + 1 day, last dose of study intervention + 1 day), end date of new anticancer therapy]

THEN imputed start date = DAY (Last day of MMM) MMM YYYY ;

• ELSE IF YYYY = Year of min [max(PD date + 1, last dose of study intervention + 1), end date of new anticancer therapy], AND

MMM = Month of min [max(PD date + 1 day, last dose of study intervention + 1 day), end date of new anticancer therapy]

THEN imputed start date = min [max(PD date + 1 day, last dose of study intervention + 1 day), end date of new anticancer therapy]);

• ELSE IF YYYY = Year of min [max(PD date + 1, last dose of study intervention + 1), end date of new anticancer therapy], AND

MMM > Month of min [max(PD date + 1 day, last dose of study intervention + 1 day), end date of new anticancer therapy]

THEN imputed start date = 01 MMM YYYY;

• ELSE IF YYYY < Year of min [max(PD date + 1, last dose of study intervention + 1), end date of new anticancer therapy]

THEN imputed start date = DAY (Last day of MMM) MMM YYYY;

• ELSE IF YYYY > Year of min [max(PD date + 1, last dose of study intervention + 1), end date of new anticancer therapy]

THEN imputed start date = 01 MMM YYYY.

#### 5.3.3.5. Other Dates

Imputation methods for other partial dates are as follows:

- If the day of the month is missing for a start date used in a calculation, the first day of the month will be used to replace the missing date;
- If both the day and month are missing, the first day of the year is used;
- For stop dates, the last day of the month, or last day of the year is used if the day or day and month are missing, respectively;

• If the date is completely missing, no imputation will be performed.

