## 3.5.1. Adverse Events

An adverse event is considered treatment-emergent relative to study intervention if the adverse event start date is during the on-treatment period (including on the date of first dose).

AEs will be as characterized by type, severity, timing, seriousness, and relationship to study intervention.

AEs (except CRS and ICANS) will be graded by the investigator according to the NCI CTCAE version 5.0. CRS and ICANS will be graded by the investigator according to the ASTCT criteria. All AEs will be coded using the most current version of Medical Dictionary for Regulatory Activities (MedDRA).

TEAEs leading to dose interruption or dose reduction will be derived from the exposure CRF (dose adjustment reason as adverse event and actual dose taken of 0 for interruption and >0 for reduction) and then linked programmatically to the adverse event CRF by the AE identifier.

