## 5.3.3. Handling of Incomplete or Missing Dates

## 5.3.3.1. Adverse Events

## AE Onset Date:

**AE Onset Date:** If the AE onset date is completely missing, and if the date of first dose is less than AE stop date, then the onset date will be assigned as the date of first dose. Otherwise if the date of first dose is after the AE stop date then the AE onset date will be imputed as the earliest of non-missing AE stop date or informed consent date.

**AE Stop Date:** If the AE stop date is completely missing then the stop date will be imputed as the latest of the participant withdrawal/completion date, death date, last dose of study intervention, or AE onset date.

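### SAP 5.3.3.1 has no rule for a partial AE onset date, and the residual rule in 5.3.3.5 would date an AE from the month of first dose before treatment and out of the TEAE summaries

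*SAP*

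**What the plan says.** Four parts of the SAP act together.

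- **AE onset (5.3.3.1).** The only branch opens "If the AE onset date is completely missing, and if the date of first dose is less than AE stop date"; onset is then set to the first-dose date. If first dose is after the stop date, onset goes to the earlier of the stop date and the consent date. The stop-date rule is likewise confined to wholly missing dates: "If the AE stop date is completely missing then the stop date will be imputed as the latest of" several dates. Nothing addresses a missing day, or a missing day and month.
- **Residual rule (5.3.3.5).** "Imputation methods for other partial dates are as follows": for a start date lacking the day, "the first day of the month will be used to replace the missing date". Also, "If both the day and month are missing, the first day of the year is used". First dose is not mentioned, and neither are AEs.
- **Treatment emergence (3.5 and 3.5.1).** An AE is treatment-emergent "if the adverse event start date is during the on-treatment period", and that period opens at first dose. The decision rests on the date alone.
- **Reporting (6.7.1).** AE analyses use TEAEs by default. Other AEs are flagged in listings.

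**The concern.** Where the partial date matches the month or year of first dose, the event could have begun before or after dosing. The residual rule always picks the earliest possible day, which is nearly always before dosing. Within the first-dose month the error therefore runs one way: true TEAEs are lost.

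The ordering is also perverse. With a stop date after first dose, an onset about which nothing is known is placed at first dose and counted, while an onset whose month is known is placed before first dose and not counted.

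The SAP protects other date types against this. A partial death date is floored at the day after last contact (5.3.3.3). A partial start date for new anticancer therapy is anchored to progression and last dose, with separate same-month and same-year branches (5.3.3.4). AE onset has no equivalent.

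At stake is the completeness of the TEAE tables, including the special-interest and clinical-interest summaries, which use TEAEs by the 6.7.1 default.

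**Working it through.** The plan states no figure to reproduce, so the check applies the rules as written.

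**Inputs.** Imputed onset is the 1st of the month, or 1 January for year-only dates (SAP 5.3.3.5). An AE is a TEAE if onset is on or after first dose and within the on-treatment period (SAP 3.5, 3.5.1). Before first dose, study day = event date − first-dose date; from first dose on, 1 is added (SAP 5.2.4).

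**Step 1: examples.** Onset known only as March:

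| First dose | Imputed onset | Study day | TEAE? |
|---|---|---|---|
| 1 March | 1 March | 1 | yes |
| 2 March | 1 March | −1 | no |
| 15 March | 1 March | −14 | no |
| 31 March | 1 March | −30 | no |

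With first dose on 15 March, a wholly missing onset and a stop date after 15 March, 5.3.3.1 gives 15 March, Study Day 1, and a TEAE.

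**Step 2: how often the imputed date is pre-dose.** Assume first-dose days are even over a 30-day month. Only the 1st escapes, so the share is 29/30 = 96.7%. An assumed calendar window of 365 first-dose days (1 February 2021 to 31 January 2022, illustrative) gives 353/365 = 96.7%. For year-only onsets in the year of first dose, only 1 January escapes: 364/365 = 99.7%.

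**Step 3: how often that is wrong.** A pre-dose imputed date is an error only if the AE truly began on or after first dose. AEs are collected from informed consent (Protocol 8.3.1) and screening runs from Day −28 (Protocol 1.3), so some of these AEs really are pre-treatment. The onset pattern is not given, so a range is needed.

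- *Onset day even over the 30 days, independent of first-dose day.* There are 30 × 30 = 900 pairs. Onset is on or after first dose in 30 × 31 / 2 = 465. Removing the 30 pairs with first dose on the 1st leaves 435 misclassified: 435/900 = 48.3%.
- *All onsets on or after first dose, with such AEs spread equally over first-dose days.* The share is 29/30 = 96.7%. If they are instead spread in proportion to the days left in the month, it is 435/465 = 93.5%.

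**Step 4: with a floor at first dose.** Taking the later of the 1st of the month and the first-dose date, 0 of the 365 first-dose days give a pre-dose onset.

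**The case against.** Several points on the other side are sound.

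- **5.3.3.5 does not name AEs.** A reader might infer that the SAP expressly directs these AEs to a pre-treatment date. It does not; applying the residual rule to AEs is an inference. SAP 5.3 says nothing is imputed unless specified, so one could hold that partial AE onsets have no rule at all. TEAE status would then be undefined, and the same sentence would still be needed.
- **CRS and ICANS.** Because CRS is expected mainly after the first doses, a reader might infer that these events would drop out. The documents point the other way. Priming doses are given to inpatients (Protocol 6.1.1), vital signs are taken at least every 4 hours after them (Protocol 8.2.3), and CRS and ICANS have dedicated case report forms (SAP 6.7.1.1). Their onset days are among the least likely to be missing.
- **Few dates may be affected.** Cycle 1 visits are frequent, SAEs are reported within 24 hours (Protocol 8.3.1.1) and source data are verified (Protocol 10.1.6). For month-known dates, only the rest of the calendar month of first dose is exposed: about 6 days for someone first dosed on the 25th of a 30-day month.
- **Counting is by participant.** Someone with another dated TEAE of the same term is still counted in that row.

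These points limit the size of the problem. They do not supply the missing rule or explain why a wholly missing date is treated more cautiously than a partial one.

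**Conclusion.** The point holds as a minor defect in a derivation rule. As the SAP reads, the only text that reaches a partial AE onset date places it before treatment whenever it shares the month (or year) of first dose, unless dosing began on the 1st (or 1 January).

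The 29/30 figure is a share of first-dose days. It should not be read as 97% of partial-date AEs being misclassified: that share runs from about 48% to 97%, and the documents do not say where in the range it lies. Both ends assume first-dose days even over a 30-day month.

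The number of partial AE dates is not given. From the way data are collected, it is probably small and mostly non-serious AEs. The primary endpoint does not use AE dates. The enrollment-hold rules (SAP 7.1.2, Protocol 9.5.2) count identified events in treated participants and are not defined through TEAE status, so the documents do not support an inference that safety monitoring is weakened.

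**What to change.** Add a partial-date branch to SAP 5.3.3.1: if the AE onset is partial and its known month and year (or year alone) match those of first dose, impute the first-dose date unless the AE stop date is before first dose; otherwise use the first day of the known month or year. This also settles whether 5.3.3.5 applies to AE onsets.

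The cost is one SAP sentence and a small program edit. The downside is that some events that truly began before dosing will count as TEAEs. If onsets were even over the month, up to (900 − 465)/900 = 48.3% of such partial-date AEs would be affected, less those that the stop date rules out. With few partial dates this means a few events, and the error is on the cautious side for safety reporting, in line with the existing treatment of wholly missing onsets.

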## 6. ANALYSES AND SUMMARIES

#### 6.1. Primary Endpoint

### 6.1.1. Main Analysis

The primary endpoint is ORR by BICR, defined as the proportion of participants with an objective response by BICR per IMWG criteria.

**Estimand strategy:** The analysis will consider intercurrent events of start of subsequent anticancer therapy (Section 2.2).

Analysis set: Safety Analysis Set (Section 4).

**Intercurrent events and missing data:** All data collected after an intercurrent event of subsequent anticancer therapy will be excluded except if required to confirm PD (Table 2). No imputations for missing data will be performed.

**Analysis methodology:** Point estimates of ORR will be calculated along with corresponding 2-sided exact 95% CIs using the Clopper-Pearson method. The null hypotheses will be tested at 1-sided alpha of 0.025 using an exact binomial test independently in each cohort, and the corresponding 1-sided p-value will be provided separately for Cohort A and Cohort B.

In addition, the frequency (number and percentage) of participants with BOR by BICR in each response category and corresponding 2-sided exact 95% CIs will be summarized: sCR; CR; VGPR; PR; MR; SD; PD; Not evaluable (NE)/unknown.

In addition, the following response categories will be calculated along with corresponding 2-sided exact 95% CIs using the Clopper-Pearson method:

- VGPR or better (sCR + CR + VGPR);
- Clinical benefit (sCR + CR + VGPR + PR + MR).

BOR by BICR will be assessed programmatically based on reported timepoint responses by BICR recorded at evaluation time points from the date of first dose until confirmed disease progression using IMWG response criteria, death or start of new anticancer therapy, whichever occurs first. BOR needs to be confirmed according to IMWG response criteria (Table 2). If a participant meets multiple criteria in determining confirmed BOR, the order of criteria in this table will be used to define the hierarchy. Twenty-eight days is the scheduled gap between the disease assessments however if done on the same day, a different sample is required for confirmation. A confirmatory response assessment may be performed >28 days following the initial response assessment, allowing for a maximum of 1 intervening missing or not evaluable assessment.

The rules for PD confirmation apply to both confirmed PD as BOR and confirmed PD after BOR (for time-to-event analyses), and the PD date is the date of the initial PD assessment.

## Table 2.Derivation Rules for Confirmed Best Overall Response per IMWG
Response Criteria

Saanaria	Timepoint Response at:							
Scenario	Assessment 1	Assessment 2	Assessment 3	DOK				
		disease under study after initiation of new anticancer therapy)						
26	$PD^b$	sCR/CR/VGPR/PR/MR/ SD/NE/PD or no further assessments	No further assessments					
27	Death (due to disease under study)							
	1	1		Γ				
28	Death (not due to disease under study)							
29	NE	No further assessment						
30	NE	NE/PD c	No further assessments	NE				
31	PD°	NE	No further assessments					

BOR= best overall response; EMD = extramedullary disease; IMWG = International Myeloma Working Group, sCR = stringent complete response, CR = complete response, PR = partial response, VGPR = very good partial response, SD = stable disease, PD = progressive disease, NE = not evaluable.

a. SD does not need to be confirmed.

- b. PD due to EMD (includes any increased or new lesion), or bone marrow plasma cells does not need to be confirmed.
- c. PD due to reasons other than EMD, or bone marrow plasma cells.

Note: category of "No Evidence of Disease" (NED) is not described in the IMWG criteria but is included in the BICR charter to cover uncommon scenarios of no measurable disease at baseline. For any such participants, post-baseline assessment of NED is equivalent to SD.

#### 6.1.2. Sensitivity Analyses

If there are participants who are enrolled but not treated in a cohort, a sensitivity analysis of ORR by BICR in all participants enrolled may be performed in the cohort. In this analysis, the untreated participants will be treated as non-responders.

#### 6.1.3. Additional Analyses of BOR

#### **BICR vs Investigator Assessment:**

Table 3 below outlines the possible BOR outcomes by investigator and BICR.

 Table 3.
 Agreement of BOR Outcomes Between Investigator and BICR Assessments

BOR		BICR Assessment							
	sCR	CR	VGPR	PR	MR	SD	PD	NE	
Investigator	sCR	n 11	n 12	n 13	n 14	n15	n 16	n 17	n 18
Assessment	CR	n 21	n 22	n 23	n 24	n 25	n 26	n 27	n 28
	VGPR	n 31	n 32	n 33	n 34	n35	n 36	n 37	n 38
	PR	n 41	n 42	n43	n44	n45	n 46	n 47	n 48
	MR	n 51	n 52	n53	n54	n55	n 56	n57	n 58

BOR		BICR Assessment							
		sCR	CR	VGPR	PR	MR	SD	PD	NE
	SD	n 61	n 62	n 63	n 64	n 65	n 66	n 67	n 68
	PD	n 61	n 72	n 73	n 74	n75	n 76	n 77	n 78
	NE	n 81	n 82	n 73	n 84	n85	n 86	n 87	n 88

 $\sum_{i=1}^{8} (n_{ii})$  is the number of agreements on BOR between BICR and Investigator

 $\sum_{i,j=1}^{8} (n_{ij})$  for  $i \neq j$  is the number of disagreements on BOR between BICR and Investigator

N=
$$\sum_{i,j}^{8} (n_{ij})$$

The following measures of agreement (n, %) will be calculated for each cohort:

- Agreement rate for BOR =  $\sum_{i=1}^{8} (n_{ii}) / N$ ;
- Agreement rate for response =  $\left[\sum_{i,j=1}^{4} (n_{ij}) + \sum_{i,j=5}^{8} (n_{ij})\right]/N$ .

Agreement rates are calculated for each metric, the high concordance rate means high agreement between BICR and Investigator.

Agreement (n, %) for BOR between BICR and Investigator will be summarized for each cohort.

ORR before and after the switch to Q2W will be summarized.

## 6.2. Secondary Efficacy Endpoints

Secondary efficacy endpoints will be analyzed in the Safety Analysis Set by cohort.

## 6.2.1. Objective Response by BICR baseline EMD Status

ORR by BICR baseline EMD status for Cohort A will be analyzed the same as the primary endpoint except separately for participants with and without EMD at baseline per BICR.

No sensitivity analyses will be performed.

## 6.2.2. Objective Response Rate by Investigator

Point estimates of ORR by investigator will be calculated along with the 2-sided exact 95% CIs using the Clopper-Pearson method. The frequency (number and percentage) of participants with BOR by investigator in each response categories will be summarized: sCR; CR; VGPR; PR; MR; SD; PD; NE.

In addition, the following response categories will be calculated along with the 2-sided exact 95% CIs using the Clopper-Pearson method:

• VGPR or better (sCR + CR + VGPR);

• Clinical benefit (sCR + CR + VGPR + PR + MR).

BOR by investigator will be programmatically assessed based on reported timepoint responses by investigator recorded at evaluation time points from the date of first dose until confirmed disease progression using IMWG response criteria, death or start of new anticancer therapy, whichever occurs first. BOR by investigator needs to be confirmed according to IMWG response criteria (Table 2).

BOR by investigator will be reassessed programmatically based on derived responses per IMWG from the date of first dose until confirmed disease progression using IMWG response criteria, death or start of new anticancer therapy, whichever occurs first. This sensitivity analysis will follow the same rules as the secondary analysis except for deriving response based on the local laboratory and bone marrow data and the individual lesion data provided by the investigator.

## 6.2.3. Complete Response Rate

CRR is defined as the proportion of participants with a sCR/CR per IMWG criteria.

Point estimates of CRR will be calculated along with corresponding 2-sided exact 95% CIs using the Clopper-Pearson method.

CRR by BICR and CRR by investigator will be summarized separately.

### 6.2.4. Progression-free Survival

PFS is defined as the time from the date of first dose until confirmed PD per IMWG criteria or death due to any cause, whichever occurs first and will be calculated as follows:

PFS (months) = [date of event or censoring - date of first dose +1] / 30.4375.

PFS will be censored as follows:

- For participants who do not have an event (confirmed PD per IMWG criteria or death due to any cause), censoring will occur on the date of the last adequate disease assessment;
- For participants who start a new anticancer therapy (as defined in Section 5.2.6) prior to an event, censoring will occur on the date of the last adequate disease assessment before the new anticancer therapy;
- For participants with an event after a gap of 2 or more missing disease assessments, censoring will occur on the date of the last adequate disease assessment before the gap;
- Participants who do not have an adequate post-baseline disease assessment will be censored on the date of first dose of study intervention unless death occurs on or before the time of the second planned disease assessment (ie, ≤70 days after the date of first dose) in which case the death will be considered an event.

The censoring and event date options to be considered for the PFS analysis are presented in Table 4. Adequate post-baseline disease assessment are defined in Section 5.2.10.

Scenario	Date of Event/Censoring	Outcome
Progression or death	Date of progression or death	Event
1. After at most 1 missing or inadequate post-baseline disease assessment or		
2. ≤70 days after date of first dose of study intervention		
Progression or death after 2 or more	Date of last adequate assessment a	Censored
missing or inadequate disease assessments"	documenting no PD prior to new	
No progression or death	assessments	
New anticancer therapy given prior to PD or death		

Table 4.Outcome and Event Dates for PFS Analyses

a. If there are no adequate post-baseline disease assessments prior to confirmed PD or death, then the time without adequate assessment should be measured from the date of first dose of study intervention; if the criteria were met, the censoring will be on the date of first dose of study intervention.

PFS = progression-free survival; PD = progressive disease

Kaplan-Meier estimates (product-limit estimates) will be presented and displayed graphically where appropriate, together with a summary of associated statistics including the median PFS time with 2-sided 95% CIs. The CIs for the median will be calculated according to Brookmeyer and Crowley, 1982.

The PFS rate at 3, 6, 9, 12, 15, 18, and 24 months (and in subsequent 12-month increments while there are participants still at risk) will be estimated with corresponding two-sided 95% CIs. The CIs for the survival function estimates at the timepoints defined above will be derived using the log(-log) method according to Kalbfleisch and Prentice (conftype=loglog default option in SAS Proc LIFETEST). The estimate of the standard error will be computed using Greenwood's formula. Frequency (number and percentage) of participants with each event type (PD or death) and censoring reasons will be presented along with the overall event and censor rates.

Reasons for censoring will be summarized according to the categories in Table 5. If a participant meets multiple definitions for censoring the list will be used to define the hierarchy.
Hierarchy	Condition	Censoring Reason
1	Start of new anticancer therapy before event	Start of new anticancer therapy
2	Event after 2 or more missing or inadequate post-baseline disease assessment after date of first dose	Event after missing or inadequate assessments a
3	No event and [withdrawal of consent date ≥ date of first dose or End of study (EOS) = Participant refused further follow-up]	Withdrawal of consent
4	No event and lost to follow-up in any disposition page	Lost to follow-up
5	No event and [EOS present or disposition page for any EPOCH after screening says participant will not continue into any subsequent phase of the study] and no adequate post-baseline disease assessment	No adequate postbaseline disease assessment
6	No event and none of the conditions in the prior hierarchy are met	Ongoing without an event

Table 5. PFS Censoring Reasons and Hierarchy

a. More than 70 days after last adequate disease assessment.

The PFS time or censoring time and the reasons for censoring will also be presented in a data listing.

PFS by BICR and PFS by investigator will be summarized separately.

If  $\geq$ 5% of participants have died due to COVID-19 related reasons, these participants will be censored at the time of death and be counted as a competing risk event in a supplementary cumulative incidence analysis.

